#### **Sample Size Calculation:**

The primary outcome for this study is a composite outcome of retention in care and maternal viral suppression that has been used in similar previous studies. This outcome was selected to measure the ultimate goal of ART use within PMTCT services: to keep HIV+ mothers engaged in care and virally suppressed to maximize the benefits of ART for both treatment and prevention. This outcome assumes that those not retained are not virally suppressed. The sample size calculation is

based on a comparison of the proportions of those in the intervention versus SOC arms reaching the combined primary endpoint at 12 months after maternal ART initiation. Pearson Chi-square test for Proportion Difference was used for calculation. A combination of various scenarios was considered for retention in care (50-90%), maternal viral suppression (50-90%) among those retained, and contamination rate (0-15%). A difference of 15% was selected as the smallest difference that would be of clinical significance. It is also assumed that an effect of this magnitude could be anticipated in this field of research.

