## Data analysis plan:

The intent to treat (ITT) population is defined as all randomized subjects, regardless of when they withdrew from the study. We will exclude the ineligible patients and thus perform modified ITT analysis as the primary analysis to facilitate interpretation if the exclusions do not disrupt the baseline equivalence established by random assignment and bias the results. We also include who completed the intervention, and with follow up data to conduct secondary and exploratory analyses of the secondary efficacy data and explorative outcomes, for example viral load, which is only available at month 6 and 12. There is no planned interim analysis for this study. All hypothesis testing will be

carried out at the 5% (2-sided) significance level unless otherwise specified. Additional ad-hoc analyses may be conducted as deemed appropriate and any changes, including the rationale for use will be documented in the clinical study report. All statistical analysis will be performed using SAS® v9.4, R 4.2.2, Stata 17 or higher for Windows.

Demography and baseline characteristics include age, socioeconomic, pregnancy and HIV variables. etc Descriptive statistics, such as, mean, standard deviation (SD) for continuous variables, and frequency and proportion for categorical variables, will be calculated by treatment group. Baseline differences will be compared using two-tailed independent t-tests (means) and chi-square tests (%) to evaluate the balance of patient characteristics in two groups by the randomization.

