The primary efficacy endpoint is the composite outcome of achievement of retention and viral suppression at Month 12. The primary efficacy endpoint will be analyzed using a binary goal attainment variable (is the achievement of retention and viral suppression [1 yes/0 no]). Participants will be considered retained in care if they are verified by clinic records as active on ART. Retention (1 Yes) will be defined as alive and attending ART clinic, as per clinic verified records, within specified window of the follow up visits. All else without known status or retention information (Due to stopped, LTFU/defaulted, transferred out, missed appointment, and missing) will be defined as Retention (0 No). Amongst those retained the study will then assess viral suppression which will be measured as viral load less than 1,000 copies per milliliter. A sensitivity analysis using detectable vs. undetectable viral load will be performed. Missing viral load information will be treated as not suppressed. There is no missing data on the primary outcome by definition.

The number and proportion of subjects who achieved retention and viral suppression at Month 12 will be summarized by treatment group. The comparison of the proportion of success in the two treatment groups will be conducted using Chi-square tests followed by logistic regression including treatment, center, and other baseline prognostic factors. Important baseline prognostic factors of the main outcome (p-values < 0.2 from univariate analysis) will be entered into the model. The main exposure variable and any factors, such as age, prior history of ART, deemed to be clinically relevant will be forced into the model regardless of the statistical significance. A backwards selection procedure will be performed to select other factors. Variables achieving statistical significance will be retained in the model. Covariates will be checked for collinearity using the variance inflation factor. Where collinearity occurs between two variables, only one of these variables will be included in the final model. An assessment of the model goodness-of-fit will be performed using the Hosmer-Lemeshow test, deviance test, and visual inspection of index plots. The adjusted odds ratio of achieving retention and adherence at Month 12 on VITAL Start versus Control will be reported along with the 95% confidence interval and 2-sided p-value.

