Secondary efficacy outcomes include achievement of retention and viral load suppression at month 6, retention at month 12, viral suppression at month 12, TFV-DP and 3TC adherence status at month 12 (for selected subcohort), and self-reported adherence status at month 12. The statistical method detailed above will be applied.

Other explorative measures include knowledge inventory, patient-Provider relationship, pregnancy intention, satisfaction with the counselling, adherence-self efficacy, partner disclosure, motivation and behavior skills, perceived social support, self-Reporting Questionnaire (SRQ)- Mental health assessment (depression and anxiety), adverse Childhood Events – International Questionnaire (ACE-IQ), cigarette use, alcohol use disorders identification test (AUDIT), drug use disorders Identification Test (DUDIT), family planning intentions, side effects, intimate partner violence (IPV), contamination measures, infant outcomes and COVID-19 impact. Descriptive statistics will be calculated for all measures and displayed by treatment group and visit as appropriate. For continuous outcomes, such as ART knowledge measures, adherence self-efficacy score, motivation and behavioral skills, perceived social support score and self-perceived patient-provider quality of HIV care score, two-

sample t-tests will be used to compare 12-month outcomes and linear mixed models will be used to examine differences in trajectories over time between the intervention and control groups. For categorical outcomes, the number and proportion of the categories at Month 12 will be compared using Chi-square tests. Generalized Estimating Equation (GEE) method for repeatedly measured categorical outcomes will be applied to compare the outcome across time between two groups while accounting for the correlation among repeated measures from the same subject.

---

**Specific aim 2: To critically examine the delivery of VITAL start** via in-depth interviews and surveys administered to patients, partners, and health workers. Adoption and satisfaction with the program will be measured. Qualitative interviews will be utilized to obtain feedback on motivational qualities of the program and benefits and challenges of delivery.

---

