Prospectively, we will collect information regarding costs of administering both the VITAL start and the SOC pre-ART counseling. To measure staff time devoted to pre- ART counseling, we will perform time-motion assessments in line with the STAMP (Suggested Time and Motion Procedures). We will sample sufficiently to account for potential sources of heterogeneity such as study clinic and provider. We will randomly sample provider sessions from each arm of the study and each participating study clinic during every month of participant enrolment. A minimum of 4 assessments will be conducted per clinic every month. Therefore, we anticipate collecting data on over 200 pre-ART counseling sessions. Repeat sampling of providers is expected and will be recorded. The value of staff time will then be estimated as the product of their gross salary and share of time allocated to intervention/pre ART counseling.

**Cost effectiveness analysis:** We will calculate incremental cost-effectiveness ratio (ICER), for the primary outcome of economic interest: proportion of women virally suppressed at 6 months follow up. The ICER is the difference in costs between two interventions divided by the difference in their effects, and can be interpreted as the incremental price of a unit health effect from the intervention under study, as compared to the alternative.

We will conduct one way and multi-way sensitivity analysis to model cost-effectiveness under various conditions, such as lower pricing of video production, mode of delivery, tablets, and alternate health care workers cadres to deliver the intervention. Finally, we will conduct probabilistic sensitivity analysis using bootstrapping methods to ascertain robustness of our results to extreme assumptions/scenarios. Based on emerging literature, we will define VITAL start as cost-effective if its ICER is < 50% of Malawi GDP ( $0.5 \times \$250 = \$125/\text{YLS}$ ), compared to standard pre-ART counseling. We will also consider alternative thresholds of 100% and 300% of GDP.

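### The plan leaves open which women form the denominator for month-12 viral suppression and for the month-6 suppression used in the ICER

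*Combined protocol and SAP*

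**What the plan says.** The Data analysis plan defines ITT as all randomised women and makes modified ITT (ineligible women excluded) the primary analysis. The next sentence is grammatically incomplete: "We also include who completed the intervention, and with follow up data to conduct secondary and exploratory analyses of the secondary efficacy data", followed by the example "for example viral load, which is only available at month 6 and 12".

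The primary-endpoint paragraph builds the composite in two steps. Women whose retention is not confirmed count as not retained. Then "Amongst those retained the study will then assess viral suppression", and "Missing viral load information will be treated as not suppressed". It closes with "There is no missing data on the primary outcome by definition".

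The secondary-outcomes paragraph lists the month-6 composite, month-12 retention and, as a separate item, month-12 viral suppression. On analysis it says only "The statistical method detailed above will be applied".

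The Sample Size Calculation section plans with "maternal viral suppression (50-90%) among those retained" and assumes, for the composite, that women not retained are not suppressed.

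Under Specific aim 3, the ICER is calculated "for the primary outcome of economic interest: proportion of women virally suppressed at 6 months follow up". That paragraph names no analysis set and no rule for missing results.

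For continuous exploratory scores, the plan compares month-12 values with two-sample t-tests and uses linear mixed models for trajectories.

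**The concern.** Three denominators for suppression can each be supported from the text: all eligible randomised women with missing counted as failure, retained women, or women who completed the intervention and have a result. They answer different questions. VITAL start is meant to improve retention, so retention and having a viral load result are consequences of assignment. Comparing arms within either subset gives up the protection of randomisation, and an effect that works by keeping women in care drops out of the comparison.

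At month 6 the choice also sets the effect in the ICER. Counselling costs arise for every woman counselled, so an effect measured only among retained or measured women does not refer to the women on whom the money was spent. If the set is not named in advance, it can be chosen after the results are seen.

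**Working it through.** **The plan's own figures.** The documents give no figure for suppression as a separate outcome. The sample size concerns the composite and is not in question. Taking 45% v 60% (an assumed control rate, since none is stated), two-sided alpha 0.025 and 90% power gives 273 per arm; 273/0.85² = 378 for contamination; 378/0.95 = 398 for attrition, as stated.

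**Inputs.** 400 per arm (800 enrolled). Month-6 retention in Table 1 at the three sites named under Study Clinics: (256 + 51 + 249)/(377 + 112 + 401) = 556/890 = 62.5%. The Study Clinics text itself gives 68-80%, so both 62.5% and 80% are used. Suppression rates and the retention gain are assumptions.

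**Formulas.** Let r0 and r1 be retention in control and VITAL start, and a and b suppression among retained women in each arm.
- Difference among retained = b − a.
- Difference among all randomised, not retained = failure: r1·b − r0·a.
- ICER = incremental cost per woman ÷ difference.

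**Effect through retention only.** Retention 10 points higher with the video; a = b = 0.90.
- Retained: 0.90 − 0.90 = 0 points; ICER undefined.
- All randomised: 0.10 × 0.90 = +9.0 points. Pooled two-proportion z-test p = 0.009 for 62.5% v 72.5%, and p = 0.003 for 80% v 90%.
- ICER = 1/0.09, about 11 times the incremental cost per woman.

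**Effect through suppression only.** Equal retention r; a = 0.85, b = 0.90.

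| r | Retained | All randomised | ICER, retained | ICER, all randomised | Ratio 1/r |
|---|---|---|---|---|---|
| 62.5% | +5.0 | +3.1 | 20 × cost | 32 × cost | 1.6 |
| 80% | +5.0 | +4.0 | 20 × cost | 25 × cost | 1.25 |

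Over the planning range of 50-90% retention the ratio runs from 1/0.5 = 2.0 to 1/0.9 = 1.1. So the restricted set understates the effect in the first case and overstates it in the second.

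**Month 12.** If non-retained and unmeasured women count as failures over the whole modified ITT set, suppression is close to the primary composite, which is reported in any case.

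**Exploratory scores.** Adjusting for a baseline value with correlation ρ narrows the interval by 1 − √(1 − ρ²): 4.6% at ρ = 0.3 and 20% at ρ = 0.6 (assumed correlations).

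**The case against.** The best defence is that the text already settles much of this. The word also may mean an additional set rather than a replacement. The sentence coding missing viral load as not suppressed names no outcome or month, and the secondary outcomes inherit the method. The month-6 secondary outcome is a composite, so it counts non-retained women as failures by definition. The ICER wording refers to women in general and reads most naturally as all women in the arm.

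Much of that stands. The month-6 composite is largely settled, and so is month-12 retention. But the missing-data coding sits in the primary-endpoint paragraph, and the method carried over may mean only the tests. If the coding did carry over, month-12 suppression would nearly repeat the composite, yet it is listed separately. None of this clearly reaches the ICER, whose effect is suppression rather than the composite.

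Stronger readings are tempting but not supported:
- **That the restricted analysis would reverse the sign.** If the extra women kept in care were suppressed at only 70%, the month-6 difference would be (1 − 0.625/0.725) × (0.70 − 0.90) = −2.8 points among retained (−2.2 at 80% v 90%), against +7.0 among all randomised. The 70% has no source in the documents, and the negative differences are not significant (p = 0.32 and 0.36).
- **That month-12 conclusions would change.** With assumed follow-up of 85% v 88% or 75% v 82%, and 50-70% suppression in the extra women, neither the measured-only differences (p = 0.18 to 0.77) nor the failure-coded ones (p = 0.13 to 0.61) reach significance. A larger retention effect would separate them: Table 1 pools to 500/912 = 54.8% at month 12, and 15 points more with 90% suppression gives 0 v +13.5. The primary composite would show that effect anyway.
- **That a cost-effectiveness decision would flip.** The threshold is $125/YLS, the effect is a proportion suppressed, and no conversion between them is given.

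The Table 1 retention input is also imperfect: Mangochi shows 46% at 6 months and 53% at 12.

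On the t-tests, they are valid, and mixed models are planned as well. Those models address trajectories and do not replace the month-12 comparison.

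**Conclusion.** The concern holds as a gap in specification, with medium confidence. The set for month-12 suppression is not named, and neither the set nor the missing-data rule is given for the ICER effect. The one sentence linking a set to viral load can be read as conditioning on completion and follow-up. It should not be read as a definite rule that replaces modified ITT.

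The month-6 ICER carries most of the weight. Under the assumed rates, the choice of denominator turns +9.0 points into 0, or changes the ICER 1.25- to 1.6-fold. These are illustrations, not predictions. At month 12 the consequence is small. The primary endpoint is untouched. The change should be made, but the trial's main result does not depend on it.

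**What to change.** 1. **Data analysis plan, population and secondary-outcome paragraphs.** State that secondary efficacy outcomes, including month-12 suppression, are analysed by assigned arm in the modified ITT set, with the primary endpoint's retention and missing-viral-load coding where viral load or retention is the outcome. State that completer, retained-only and measured-only results are supportive.
2. **Cost effectiveness analysis.** State that month-6 suppression in the ICER uses the same set and coding, so that cost and effect refer to the same women.
3. **Separately, exploratory scores with a baseline value** (knowledge, motivation, self-efficacy, social support). Replace the unadjusted month-12 t-test with a month-12 contrast adjusted for baseline value and clinic. This is a free gain in precision, about 5-20% narrower intervals if the baseline correlation is 0.3-0.6. It does not correct an error.

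The cost is a few sentences and a little analysis on data already collected. The downside is that month-12 suppression coded this way largely repeats the primary composite, so the retained-only figure should still be shown, labelled supportive. Multiple imputation is not needed to close the gap.

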For the primary analysis in all subjects, accounting for up to a 15% contamination rate (pilot data suggests 0% contamination) and assuming 1:1 allocation ratio, and 5% attrition (based on transfer out rates from Ministry of Health data at study clinics in 2016) to achieve 90% power to detect a minimum difference of 15% between the control and intervention group, 796 subjects are required (398/398 per arm) at a significance level=0.025 to account for multiple comparisons. Given the anticipated policy change to a dolutegravir-based regimen in the near future, we have further increased the sample size by 12%, to 446 per arm. This increase was done due to published evidence demonstrating higher rates of viral suppression and lower rates of discontinuation in patients on dolutegravir-based regimens. We increased the sample size because this would make a difference between our study and control groups more difficult to measure. We will also plan to have a small pilot of new trial tools and procedures. We estimate that approximately n= 30 to 50, will be needed for adequate piloting. However, given much less contamination than anticipated and disruptions caused by the COVID-19 pandemic which culminated in complete suspension of enrollment from April through July 2020, the study enrolled 800 participants in total.

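### The primary analysis is sized at 0.025 but tested at 5%, and the plan does not say which of its two p-values decides or what would overturn the modified intention-to-treat population

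*Combined protocol and SAP*

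**What the plan says.** **Level.** Under Sample Size Calculation, the number needed for the primary analysis was derived "at a significance level=0.025 to account for multiple comparisons". Neither the comparisons nor the sidedness is stated. The Data analysis plan says that all tests are "carried out at the 5% (2-sided) significance level unless otherwise specified". Its text on the primary endpoint gives no other level, and the adjusted odds ratio "will be reported along with the 95% confidence interval and 2-sided p-value".

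**Test.** The comparison of success proportions at Month 12 "will be conducted using Chi-square tests followed by logistic regression including treatment, center, and other baseline prognostic factors". For sizing, "Pearson Chi-square test for Proportion Difference was used for calculation". The sizing target is on the risk-difference scale: "A difference of 15% was selected as the smallest difference that would be of clinical significance". Randomisation is stratified by clinic (Randomization and allocation concealment); the chi-square is not.

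**Covariates.** "Important baseline prognostic factors of the main outcome (p-values < 0.2 from univariate analysis) will be entered into the model". In addition, "any factors, such as age, prior history of ART, deemed to be clinically relevant will be forced into the model". The remaining factors are reduced by backward selection, keeping those that reach significance.

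**Population.** The Data analysis plan removes ineligible women and makes this modified intention-to-treat set primary, provided that the removal neither upsets the balance created by randomisation nor biases the results. It gives no measure of either, no decision-maker or timing, and no population to use if the condition fails.

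**The concern.** A confirmatory analysis needs its threshold, test, model and population fixed before the arms are compared. Here the stricter level was used to set the size of the trial and does not reappear where the result is judged, so the same data can be read as a success or a failure. The chi-square and the adjusted model each produce a p-value for the same endpoint, and nothing ranks them. The sizing points to the chi-square, while the reporting commitment (odds ratio, interval, p-value) points to the model. The secondary outcomes take over the same method, so the ambiguity carries to them.

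**Working it through.** **1. Was 0.025 really used for sizing?** Inputs from Sample Size Calculation: 90% power, 15 points, 15% contamination, 5% attrition, 398 per arm. The control rate is not given; I assume 45%. I also assume that contamination means 15% of controls gain the full effect, so the control rate becomes 0.45 + 0.15 × 0.15 = 0.4725 against 0.60, a difference of 0.1275.

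n = [z(α/2)·√(2p̄(1−p̄)) + z(β)·√(p₁(1−p₁) + p₂(1−p₂))]² / d², with p̄ = 0.53625 and z(β) = 1.2816.

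- Two-sided 0.025 (z = 2.2414): (2.2414 × 0.7052 + 1.2816 × 0.6995)² / 0.1275² = 377.5, so 378. Then 378 / 0.95 = 398, the plan's figure, and 398 × 1.12 = 446. Control rates of 35 to 50% give 389 to 400.
- Two-sided 0.05 (z = 1.9600): 320, and 320 / 0.95 = 337.

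So two-sided 0.025 was very probably built into the sample size.

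**2. How far apart are the two thresholds?** The plan reports 800 enrolled; I take 400 per arm. With a pooled rate of 50%, SE = √(2 × 0.25 / 400) = 0.03536.

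- 5%: 1.960 × 0.03536 = 6.93 points.
- 0.025: 2.241 × 0.03536 = 7.92 points.

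At pooled rates of 60% and 70% the windows are 6.79 to 7.76 and 6.35 to 7.26 points. In counts (Pearson, no continuity correction):

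| Successes | Difference | p |
|---|---|---|
| 213 vs 186 | 27 | 0.056 |
| 214 vs 186 | 28 | 0.048 |
| 215 vs 184 | 31 | 0.028 |
| 216 vs 184 | 32 | 0.024 |

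An excess of 28 to 31 successes is therefore positive at one level and negative at the other.

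**3. How likely is that?** Exact binomial probability of passing at 5% but not at 0.025, 400 per arm, control assumed 55%:

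| True difference (points) | Probability |
|---|---|
| 7 | 11.2% |
| 8 | 11.0% |
| 10 | 8.2% |
| 12.1 | 4.1% |
| 15 | 0.8% |

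Control rates of 45% or 50% change these by about half a point at most. The 12.1 is 15 × 0.85 × 0.95: the planned effect diluted by 15% contamination and by 5% transfers counted as failures, as the endpoint definition requires.

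**4. Does the covariate selection itself inflate error?** This was simulated under no effect: 800 women, 3 clinics, 15 to 33 candidate covariates, the p<0.2 screen and then backward selection. Covariate numbers and strengths are assumptions. At 5%, the chi-square rejected in 4.7 to 5.7% of runs and the selected logistic model in 4.5 to 5.9%. Counting a trial as positive if either test passed gave 6.3 to 8.2%. With a true effect and six prognostic covariates (assumed log odds ratio 0.15 to 0.50 per SD), the two tests disagreed at 5% in 7 to 16% of trials at 8 points, 3 to 10% at 10 points and about 0.5% at 15.

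**The case against.** The best defence reads the plan as already consistent. The 5% level yields where another is specified, and the sizing sentence is expressly about the primary analysis in all subjects, so 0.025 could be the exception. That reading is possible. But the 0.025 appears only in the sizing text, and the primary analysis then commits to a 95% interval, which belongs to 5%. Taking 0.025 as one-sided, and so equal to 5% two-sided, does not fit either. The stated reason is multiple comparisons, and two-sided 5% with contamination of controls only reaches at most 338 per arm. It gives 398 only with contamination in both arms and a control rate of 65%.

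It can also be said that the chi-square is implied, being first in order and the basis of the sizing. That is fair, but it is not designated, and the reporting sentence points to the model.

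Safeguards count too. Allocation is entered only after data collection, the statistician and lead researcher stay blinded, and changes must be documented with reasons. These reduce the risk of a data-driven choice. They do not remove it, because a two-sided p-value is the same whichever coded arm is the intervention.

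Finally, the disputed window lies at about half the difference that the plan calls clinically important, and at a true 15 points it hardly matters. That stands and limits the weight of the point.

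**Conclusion.** The point holds as a specification gap that should be closed. The documents give two success thresholds about one percentage point apart, two undesignated p-values, and a conditional primary population without a rule. The threshold conflict is the firmest part. The probabilities assume 400 per arm and control success near 55%; the reproduction of 398 rests on an assumed control rate and contamination model.

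A reader might infer more than the documents support:

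- *That the covariate selection inflates type I error.* In simulation each test alone stays close to its level. The 6 to 8% arises only if either test may count, which the plan does not say.
- *That the modified intention-to-treat condition cannot be checked.* Baseline balance tests are planned, and full intention-to-treat is a natural fallback. What is missing is a stated criterion and a stated fallback. Balance tests alone also cannot show that results are unbiased.
- *That prior ART history was never collected.* It is absent from the baseline items listed in the protocol, but the draft questionnaire said to be attached is not in the text available, so it may be there.

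**What to change.** Issue a dated amendment before allocation is entered into the data set:

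- **(a) Alpha.** State one level with a matching interval: either 0.025 with a 97.5% interval, as sized, or 5% with a 95% interval and an explanation of which comparisons the 0.025 was for.
- **(b) Deciding test.** Name one: the chi-square used for sizing, or a clinic-stratified version such as a Mantel-Haenszel risk difference. The stratified version matches the randomisation and reads directly against the 15 points, but performed almost the same in simulation, where clinic differences were assumed small. All other analyses become supportive.
- **(c) Covariates.** Replace the p<0.2 screen and backward selection with treatment, clinic and a short closed list of variables confirmed as collected at baseline. Include prior ART history only if it was recorded.
- **(d) Population.** Make all randomised women primary and modified intention-to-treat a sensitivity analysis, with ineligibility judged blind to arm from facts that predate randomisation.

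If allocation has already been entered, keep the chi-square as the deciding test and label the other changes post hoc.

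Cost: no new data. Making the adjusted model supportive only may give up power: about 1 to 6 percentage points at a true 12.1 points and alpha 0.025, depending on the assumed covariate strength. Keeping ineligible women dilutes the effect slightly. Enrolment is complete, so the amendment is late, and its timing relative to allocation must be documented.
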